1.4 STUDY PLAN

The following figure describes an overview of the design of the study:

Figure 1 – Study Design

The study consists of:

- Screening period will be up to 21 days
- Treatment period is 14±1 days
- Follow up period will be 14±2 days
- Total study duration will approximately be 26-51 days

1.5 MODIFICATIONS FROM THE STATISTICAL SECTION OF THE PROTOCOL

This SAP describes updated standard analyses as planned in the new BTD-009094.

1.6 STATISTICAL MODIFICATIONS MADE IN THE STATISTICAL ANALYSIS PLAN

Not applicable

2 STATISTICAL AND ANALYTICAL PROCEDURE

2.1 SUBJECT DESCRIPTION

2.1.1 Disposition of subjects

A detailed description of patient accountability will be generated by treatment group, including count of:

- Screened patients (i.e. having signed the informed consent);
- Screen failure patients and reason for screen failure;
- Patients randomized and treated (i.e. randomized patients with a treatment number assigned and recorded and received at least one administration of IMP);
- Patients who permanently discontinued the IMP with the main reason for permanent treatment discontinuation,
- Patients who requested permanent treatment discontinuation.

Patients treated without being randomized will not be considered as randomized and will not be included in any analysis population for which being randomized is required. The safety data of patients treated but not randomized will be reported separately, and these patients will not be in the safety population.

Additionally a count of screened patients including number of screened patients, screen failure and inclusion/exclusion criteria met will be provided.

A listing of patients with treatment discontinuation or screen failure will be provided sorted by treatment group and patients, including patients status at the end of the study with the date of last IMP administration, date of last available information and method of contact, reason for permanent treatment discontinuation, and whether the blind was broken on site at time of discontinuation. All withdrawals from the study, taking place on or after IMP administration, will be fully documented in the body of the clinical study report (CSR).

In case of code broken for medical and accidental reasons on site, a listing of concerned patients will be provided, specifying the reason (AE/SAE or other), the date and time of code breaking, and the person who broke the code.

A listing of all comments done by the Investigator on the electronic case report form (eCRF) will be provided by treatment group, if any.

2.1.2 Protocol deviations

During the blinded review of the database, compliance with the protocol will be examined with regard to inclusion and exclusion criteria, treatment or dosing compliance, prohibited therapies, and timing and availability of planned assessments. Protocol deviations will be identified by the study team before database lock and listed in the Data Review and Surveillance Report, including missing data and study drug discontinuations, and classified as critical, major or minor deviations.

Critical or major deviations resulting in exclusion for the pharmacodynamics analyses and any other critical or major deviations will be summarized by treatment group.

2.2 ANALYSIS POPULATIONS

The number of patients included in each study population (safety population, pharmacokinetic population, pharmacodynamic population, pharmacokinetic/pharmacodynamic population) will be provided by treatment group. All exclusions from any analysis populations (pharmacodynamic, pharmacokinetic, and/or safety) will be fully documented in the clinical study report.

2.2.1 Pharmacodynamic population

For the main PD endpoints of plasma volume and hemoconcentration, the PD population will consist of all randomized and treated patients who have valid values of the main PD parameters both at baseline and at Day 14/EOT.

2.2.2 Safety population

All randomized patients who are exposed to IMP (regardless of the amount of treatment administered) will be included in the safety population. For safety analyses, patients will be included in the treatment group as actually received. Non-randomized and treated patients will not be part of the safety population, but their safety data will be summarized separately.

2.2.3 Pharmacokinetic population

The PK population will consist of all patients in the safety population who have at least one non-missing and eligible plasma concentration data.

Only patients with no major or critical deviations related to IMP (eg, vomiting just after drug administration), and for whom PK data are considered sufficient and interpretable, will be included in the pharmacokinetic population.

Patients will be analyzed according to the treatment actually received. Patients having received only placebo will not be included in the pharmacokinetic population.

2.2.4 Pharmacokinetic/Pharmacodynamic population

All patients being included in both the pharmacokinetic and the pharmacodynamic populations will be included in the pharmacokinetic/pharmacodynamic population. In addition, patients being included in the pharmacodynamic population and having received only placebo will also be included in the pharmacokinetic/pharmacodynamic population.

2.3 DEMOGRAPHIC AND BASELINE CHARACTERISTICS

2.3.1 Subject demographic characteristics, medical history, and diagnoses

The response to IMP might be affected by several variables, including continuous variables (e.g., age, height, weight, body mass index (BMI) and qualitative variables (gender, race and/or ethnicity). BMI can be described both quantitatively and qualitatively (Underweight: BMI is less than 18.5; Normal weight: BMI is 18.5 to 24.9; Overweight: BMI is 25 to 29.9; Obese: BMI is 30 or more). The following variables will be summarized by descriptive statistics for the safety population and for additional population if relevant:

- Age (years)
- Weight (Kg)
- Height (cm)
- Body mass index (Kg/m²)
- Race and/or ethnicity
- Gender
- eGFR

Medical history will be coded according to MedDRA (last version available before database lock). Specific medical history (Diabetes, cardiovascular events – including but not limited to stroke, myocardial infarction, atrial fibrillation – and previous cardiac interventions (eg angioplasty)) will be summarized by treatment group and overall, and presented by primary SOC and High Level Term (HLT) on the safety population. The events will be sorted by SOC internationally agreed order and decreasing frequency of HLT.

2.3.2 Baseline pharmacodynamic parameters

Baseline values of PD parameters are defined to be those taken or measured approximately one to three (3) hours prior to the first dosing of study treatment on Day 1.

All baseline PD parameters will be summarized and presented by treatment group as with all other baseline patient characteristics. In addition, for the main PD parameters such as plasma volume and hemoconcentration, the mean baseline values of the PD parameters will also be summarized along with the mean Day 14/EOT values and mean change from baseline values.

2.3.3 Baseline safety parameters

Baseline for safety parameters will be defined as the last available and evaluable parameter value before and closest to the first IMP dosing for laboratory data, vital sign parameters, and for 12 lead ECG parameters.

Baseline definitions specific to each type of safety parameter will be detailed in corresponding [Section 2.7.2 to Section 2.7.5](#)

Baseline safety values will be presented along with subsequent safety values assessed during or after dosing.

2.4 EXTENT OF STUDY TREATMENT EXPOSURE AND COMPLIANCE

The extent of study treatment exposure (ie, duration of IMP exposure during the study) will be defined as the total number of days of IMP administrations, ignoring temporary drug discontinuations and will be calculated as:

$(\text{Date of the last study drug administration} - \text{date of the first study drug administration}) + 1$.

The duration of IMP exposure during the study will be summarized categorically (counts and percentages) by treatment group, on the safety population using the following categories: between 1 and 7 days; between 8 and 11 days; between 10 and 12 (excluded) days; between 12 and 15 days.

The following listings will be provided:

- Patients receiving IMP from specified batch
- Randomization scheme.

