### 12.3 REPLACEMENT OF PATIENTS

According to the study design, a patient who prematurely ends his/her study period after the start of the baseline period and who received treatment may be replaced in order to have 81 patients who have completed a minimum of 12 days treatment with IMP (sotagliflozin or placebo).

In the case of a discontinuation related to an AE, the replacement may be discussed between the Investigator and the Sponsor.

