### **14.5 EXTENT OF STUDY TREATMENT EXPOSURE AND COMPLIANCE**

A summary table presenting the exposure of treatment (ie, the number of days of administration and number of tablets taken, etc) will be provided by treatment group for the safety population.

The following listings will be provided:

- Patients receiving IMP from specified batch
- Randomization scheme.

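### The exposure-duration categories in SAP 2.4 are not mutually exclusive: a patient with exactly 10 or 11 days of treatment fits two rows

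*SAP*

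**What the plan says.** SAP 2.4 defines duration of exposure as the date of last dose minus the date of first dose, plus 1, ignoring temporary interruptions. For each arm of the safety population, the table then gives the number and percentage of patients in each of four bands, which the section sets out as "between 1 and 7 days; between 8 and 11 days; between 10 and 12 (excluded) days; between 12 and 15 days".

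The protocol does not supply alternative bands. Its section 14.5 promises "A summary table presenting the exposure of treatment (ie, the number of days of administration and number of tablets taken, etc") by treatment group, with no categories of duration. The general data-handling rules in SAP 2.9 do not cover a patient who fits two rows of a table. Neither document says that the exposure rows are cumulative or meant to overlap.

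Two other statements bear on the point. SAP 1.4 gives the planned duration: "Treatment period is 14±1 days". Protocol 12.3 allows replacement so as to reach a target number of patients who have "completed a minimum of 12 days treatment with IMP".

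**The concern.** A table of counts and percentages by duration band is normally read as a partition: each patient appears once, and the rows add to the safety population of that arm. These four bands do not form a partition. A programmer who follows the text exactly will produce rows that can sum to more than N. A programmer who notices the problem must choose a row without guidance, so two people could produce different tables from the same data.

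Safety and tolerability is the trial's primary objective, and the exposure table is the background against which adverse events are read. The affected patients would be early stoppers, who remain in the safety population. Such durations are plausible, because re-hospitalization ends study treatment under protocol 7.2.1 and 8.1.

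**Working it through.** **Inputs.** The four bands and the duration formula come from SAP 2.4. Because the formula is a difference of dates plus 1, duration is always a whole number of at least 1. Arm sizes come from Table 1 of the amended protocol (200 mg 10, 400 mg 27, placebo 27, total 64) and from Table 1 of the SAP (27 in each of three arms, total 81).

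**Step 1: assign each whole-day duration to the bands as written.**

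| Duration (days) | 1-7 | 8-11 | 10 to <12 | 12-15 | Rows matched |
|---|---|---|---|---|---|
| 1 to 7 | yes | | | | 1 |
| 8, 9 | | yes | | | 1 |
| 10, 11 | | yes | yes | | 2 |
| 12 to 15 | | | | yes | 1 |

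The third band is the set {10, 11}, which lies wholly inside the second band {8, 9, 10, 11}.

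**Step 2: try other readings of the bounds.**
- If both ends of the third band are excluded, day 11 still matches two rows.
- If the upper end of the second band is excluded, day 10 still matches two rows.

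Neither reading removes the overlap.

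**Step 3: size per affected patient.** One extra count in an arm of size n adds 100/n percentage points to the column total.
- Arm of 27 (400 mg or placebo in either document; 200 mg in the SAP): 100/27 = 3.7 points.
- 200 mg arm of 10 (amended protocol): 100/10 = 10 points.
- All patients: 100/64 = 1.6 points on the amended protocol's total, or 100/81 = 1.2 points on the SAP's.

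As an illustration only, two such patients in an arm of 27 would make the rows sum to 29, or 29/27 = 107.4%.

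**Step 4: check the candidate corrections.** With 1-7, 8-9, 10-11 and 12-15, every duration from 1 to 15 days matches exactly one row. The same holds for 1-7, 8-11 and 12-15. Fifteen days is the planned maximum (14 + 1).

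**The case against.** Several points can fairly be made on the other side.

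- **The double count is conditional.** It needs at least one patient with exactly 10 or 11 days and a programmer who fills the rows literally. With 14±1 days planned, only early stoppers can be affected, and there may be none. This stands.
- **The 12-day limit is not involved.** A reader might infer that the overlap blurs who counts as having reached 12 days, and hence who may be replaced. The documents do not support that. The 12-15 day row overlaps nothing, and a patient with 10 or 11 days is below 12 in either row. Replacement is decided under protocol 12.3, not from this table. SAP 1.3 describes completers by plasma volume values at baseline and end of treatment, not by days of exposure.
- **It is not the only source on exposure.** A reader might take this as the trial's sole exposure output. Protocol 14.5 plans a wider summary that includes tablets taken. SAP 2.1.1 lists discontinued patients with their last dose date, and SAP 2.9 provides listings of all individual data. Correct counts could be rebuilt.
- **The denominators are uncertain.** The 10-point figure uses the amended protocol's 200 mg arm, whereas the SAP was written for 27 in that arm. The table runs on the safety population, which may hold both early stoppers and their replacements. This stands, so the figures are per-patient illustrations.
- **It is unclear which band is the slip.** The 8-11 day band coincides with the Visit 4 window in SAP Appendix A (Day 8 to Day 11), so the third band may be the stray one. Equally, the upper bound of the second may be mistyped. The documents do not settle it.

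None of this removes the overlap in the text.

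**Conclusion.** The point holds as a minor error in an operative tabulation rule. As written, durations of 10 and 11 days belong to two categories. Applied literally, each such patient inflates the column total by 3.7 percentage points in an arm of 27, or by 10 points in a 200 mg arm of 10. These sizes assume planned arm sizes; the number of affected patients cannot be known from the documents and may be zero. No primary estimate, power, error rate, analysis population or replacement decision depends on this table, and the count of patients reaching 12 days remains right. The matter is one of a correct and reproducible descriptive table.

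**What to change.** Before database lock, restate the bands in SAP 2.4 as mutually exclusive whole-day ranges with both ends included. Either of these works:

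- 1-7, 8-9, 10-11 and 12-15 days, which keeps the SAP's third band and shortens the second; or
- 1-7, 8-11 and 12-15 days, which drops the third band and keeps the second.

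Both keep the 12-day cut. The choice is the sponsor's, since the documents do not show which was intended. The cost is one line in the SAP and the matching line in the table specification; no data collection or other analysis changes.

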2.5 PRIOR/CONCOMITANT MEDICATION/THERAPY

Medications will be coded according to the World Health Organization Drug Dictionary (Drug Dictionary (WHO-DD), last available version before database lock). Summary of concomitant medications with the IMP will be provided by anatomic class and therapeutic class.

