**Population:** The population will include patients with pre-existing heart failure who have been hospitalized with worsening of their heart failure, and have been stabilized sufficiently to be switched from IV to oral diuretic therapy (post-worsening heart failure). Patients who present with worsening of heart failure are treated initially with IV diuretics due to reduced absorption of oral diuretics in the acute heart failure state (5). Once the signs and symptoms of worsening heart failure have improved, therapy is switched from IV to oral diuretic therapy in preparation for chronic outpatient treatment. The switch from IV to oral diuretic therapy represents a point in the clinical course when the signs and symptoms of volume overload have improved although the plasma volume remains increased and further reduction is achieved with oral diuretic therapy. This post-worsening population is more clinically stable and whereas volume overload persists, is suitable for assessing safety and pharmacodynamics (PD) efficacy of SGLT inhibition in heart failure. The limitations of this population include ongoing fluctuations of renal function and the limited published data on plasma volume change and hemoconcentration in this setting (6)(7)(8). Hemodynamic perturbations and pharmacotherapy during acute heart failure impact renal function and this period of flux makes renal function both vulnerable to toxic insults and difficult to assess for trends. Chronic kidney disease (CKD) is common in the heart failure population. It is anticipated that approximately 50% of patients with post-worsening heart failure may have an eGFR of  $<60\text{mL}/\text{min}/1.73\text{m}^2$  (9). Sotagliflozin (400 mg) was well-tolerated in patients with stage 3 CKD for a period of 7 days. Patients with an eGFR of  $<30\text{mL}/\text{min}/1.73\text{m}^2$  will be excluded from the study.

**Dose:** There are no published data to support the safety and tolerability of SGLT inhibition in patients who are hospitalized with worsening of heart failure. SGLT inhibition is known to reduce blood pressure and glomerular filtration rate (GFR) in healthy subjects and in patients with diabetes. Sotagliflozin causes a dose-dependent reduction in blood pressure.

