## 9.8 CONCOMITANT MEDICATION

A concomitant medication is any treatment received by the patient concomitantly to any IMP(s). The IMP includes placebo and sotagliflozin 200 mg and 400 mg.

All concomitant medications should be documented on the concomitant medications and herbal therapies page of the e-CRF. This includes all non IMP treatments that are taken by the patients at any time during the clinical study, beginning Day 1.

Additionally, a history of all medications in the 3 months prior to Day 1 should be taken.

An accurate record of all concomitant medications must be entered in the eCRF, including the name of the medication (INN), daily dosage, and duration of use.

Doses of chronically administered medicines should be kept fixed during the trial if at all possible. Special consideration should be given to the following:

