### **Diuretics**

Co-administration of IMP with loop and thiazide diuretics might lead to clinically significant volume depletion.

Modifications to the dose of the loop and/or thiazide diuretic might be necessary. The Investigator should consult with relevant experts (e.g., nephrologists) as appropriate. For patients with a systolic blood pressure  $< 110$  mm Hg at Randomization, the doses of any diuretic or other antihypertensive medication may be decreased in order to prevent possible hypotension.

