#### 13.1.2 Inclusion procedures

Inclusion procedures will be carried out during Screening (D-21 to D-1) or D1, as appropriate for each patient. Those will include the investigations listed in the study flow chart ([Section 1.2](#)) and detailed in [Section 10.2](#).

Baseline parameters may be rechecked once, at the Investigator's discretion. Results of a rechecked value should be known before the inclusion. The last value should be considered as the baseline value and reported in the case report form.

Prior to final inclusion and randomization, all patients must have completed the last planned IV administration (bolus or infusion), and *either* have commenced oral diuretic therapy *or* have a clear and documented plan to commence oral diuretic therapy. Patients may be discharged and return for Day 1 procedures within seven (7) days from discontinuation of IV diuretic administration.

Final inclusion and randomization, as appropriate, will be performed just before commencement of procedures on Day 1. Each patient will receive an incremental identification number corresponding to his/her order of enrollment in the study.

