1.3 DETERMINATION OF SAMPLE SIZE

The sample size determination and the statistical power are estimated based on the main PD endpoint of plasma volume. The following assumptions are used for the estimation of the sample size, based on published data of the plasma volume (PV) response following 12 weeks of treatment with SGLT2 inhibition, relative to the placebo response, in non-HF patients:

- 10% reduction in plasma volume from baseline, with an averaged value of 0.47 liters difference for the sotagliflozin group to the end of 2-week treatment between the sotagliflozin and placebo groups, respectively;
- The placebo response might be highly variable in this population. In the study by Lambers Heerspink et al, PV increased by approximately 2% at the end of the 12 week treatment period in the non-HF population. For the purpose of sample size estimation in this study, the assumption is that PV will be reduced by 1% in the placebo group.
- A common standard deviation (SD) of 0.8 liters for the reductions from baseline to the end of 2-week treatment in plasma volume for both groups;
- A t-test at 1-sided $\alpha=0.05$; or equivalently, 2-sided $\alpha=0.10$;

Based on the above assumptions, it is estimated that, with a total of 81 patients with complete evaluations, or 27 patients per arm, the study will have a 71% power to detect an approximately 9 percentage point difference (10% vs 1%) in the reduction from baseline in plasma volume at the end of 2-week treatment for the main comparison of the pooled sotagliflozin (200 mg and 400 mg) group versus placebo. With 60 evaluable patients, or 20 patients per group, the study power is 60%. The calculated sample size refers to the size of completers who have plasma volume values at both baseline and end of the 2-week treatment.

[figure not shown]
Furthermore, interim analyses will be performed following Cohort 2 and during Cohort 3 for the purpose of exploratory analyses of pharmacodynamic, pharmacokinetic or safety variables, and sample size re-estimation, partly based on the observed variability of changes in plasma volume and/or hemoconcentration. Exploratory analyses may also be performed earlier for safety reasons, or if requested by the DMC or institutional ethics committees. In that case, the analysis will not result to any changes to the protocol.

The study population will consist of at least 30% diabetic patients.

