2.6.2 Primary analysis

The main pharmacodynamic variables, change from baseline to Day 14 in hemoconcentration and plasma volume, will be analyzed using an analysis of covariance (ANCOVA) model with fixed terms for treatment and stratification factor of baseline patient status (diabetic, non-diabetic, ejection fraction status (reduced-preserved), and with baseline plasma volume as covariate. An estimate for the between-group difference in treatment mean changes and corresponding 2-sided 90% confidence interval (CI) will be calculated from the model. The main treatment comparison will be between the pooled treatment (200 mg and 400 mg) group and placebo which will be made at 1-sided $\alpha=0.05$ (or equivalently, 2-sided $\alpha=0.10$).

No multiplicity procedures will be applied as the study is exploratory in nature.

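### No planned summary shows whether diuretic dose changed differently by arm, so a small or null plasma-volume difference would be hard to interpret

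*SAP*

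**What the plan says.** **Reporting.** SAP 2.5 gives one output for concomitant drugs: "Summary of concomitant medications with the IMP will be provided by anatomic class and therapeutic class". It plans no table of diuretic dose, dose change or IV diuretic use by arm.

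**Data collected.** Protocol 9.8 requires an eCRF record of each drug "including the name of the medication (INN), daily dosage, and duration of use". Protocol 14.6 plans by-subject medication listings, and SAP 2.9 plans listings of all individual data sorted by treatment group.

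**Diuretics during the trial.** Inclusion criterion I 07 requires that oral diuretic treatment has been prescribed or given. Protocol 9.8 asks for chronic medicines to be kept at fixed doses where that can be done. Its Diuretics paragraph then warns of volume depletion when study drug is combined with loop or thiazide diuretics, and says their doses may need to be modified. For patients with SBP below 110 mm Hg at randomization it adds that "the doses of any diuretic or other antihypertensive medication may be decreased in order to prevent possible hypotension".

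**Timing of baseline.** Patients may return for Day 1 procedures "within seven (7) days from discontinuation of IV diuretic administration". Protocol 4.2.2 describes the switch to oral therapy as a time when symptoms have improved "although the plasma volume remains increased and further reduction is achieved with oral diuretic therapy".

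**Model.** The ANCOVA in SAP 2.6.2 has terms for treatment, diabetes status and ejection fraction status, "with baseline plasma volume as covariate". It has no diuretic term.

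**The concern.** Plasma volume is a co-primary objective, and background diuretics act on it directly. Protocol 4.2.3 says standard diuretic therapy may lower plasma volume by up to 25% in patients hospitalised with worsening heart failure; the SAP's target difference is 9 percentage points. If study drug adds to volume depletion and investigators respond by cutting diuretics, cuts could be more common on active drug and part of the drug's own effect on plasma volume would be offset.

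A class-level table cannot show this. Because of I 07, almost every patient in both arms will appear as a diuretic user, whether the dose was held, halved or stopped. A reader faced with a small difference would not know from any planned summary whether the drug did little or whether background treatment moved the other way.

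A separate and smaller point concerns precision. Baseline is measured at varying times, 0 to 7 days after the last IV diuretic, while decongestion is still going on. That interval may explain some of the variation in change from baseline, and the model does not use it.

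**Working it through.** **1. The plan's own figure.** Inputs from SAP 1.3:
- "A t-test at 1-sided" alpha of 0.05
- "A common standard deviation (SD) of 0.8 liters for the reductions from baseline"
- a 10% reduction, given as 0.47 L, on sotagliflozin
- a 1% reduction on placebo

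Implied baseline: 0.47 / 0.10 = 4.7 L. Implied difference: 0.09 × 4.7 = 0.423 L.

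Pooled comparison, 54 v 27: SE = 0.8 × √(1/54 + 1/27) = 0.189 L. Noncentral t power is 71.9%, against 71% stated. With 40 v 20 it is 60.4%, against 60% stated. Both figures reproduce, so 0.423 L is a fair reading of the planned difference. (Using 0.47 L at 54 v 27 gives 79.6%, which does not match.)

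**2. Current size.** Table 1 of the current protocol has 10 + 27 = 37 on sotagliflozin and 27 on placebo. SE = 0.8 × √(1/37 + 1/27) = 0.202 L, and power under the same assumptions is 66.3%.

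**3. How far differential diuretic cuts could shrink the difference.** The documents give no rates, so everything here is assumed. Take cuts in 30% of active and 10% of placebo patients, an excess of 0.20.

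Attenuation = 0.20 × (rise in plasma volume per cut).

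- *Small case.* In the trial cited in Protocol 4.2.3, in diabetic patients without heart failure, plasma volume rose 2.8% on hydrochlorothiazide and 5.2% on placebo, a gap of 2.4 points. On 4.7 L that is 0.024 × 4.7 = 0.113 L. Attenuation = 0.20 × 0.113 = 0.023 L, and 0.023 / 0.423 = 5%.
- *Larger cases.* With 0.3 L per cut: 0.20 × 0.3 = 0.06 L, or 14% of 0.423. With 0.5 L per cut: 0.20 × 0.5 = 0.10 L, or 24%.

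**4. What that means for power at 37 v 27.** With no attenuation it is 66.3%. With 10% attenuation (0.381 L) it is 58.5%. With 25% (0.317 L) it is 46.2%.

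**5. Adding days since the last IV diuretic.** SE ratio = √(1 − R²), where R² is the assumed share of variance in change that the covariate explains. For R² = 0.05, √0.95 = 0.975, so the SE falls 2.5%. For R² = 0.15, √0.85 = 0.922, so it falls about 8%. This is a gain in precision only and does not undo the attenuation in step 3.

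**The case against.** Much can be said for the plan as it stands.

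- **The changes can be found.** A reader might infer that diuretic changes would go unseen. They would not: daily dose is in the eCRF, the diary records changes in medication (Protocol 9.10), and by-subject listings are planned for about 64 patients. What is missing is a summary by arm, which raw listings of patients on several drugs do not readily supply.
- **The estimate is valid for its question.** The objective is the effect of sotagliflozin added to standard of care. The as-randomised contrast, with whatever diuretic adjustment follows, estimates that. The co-primary question is therefore answered; isolating a direct effect is a further question.
- **The SBP provision is not a differential trigger.** It depends on blood pressure at randomization, so eligibility for it is balanced in expectation. The argument for unequal cuts rests on the general volume-depletion warning, together with the paragraph on antihypertensives. Neither gives a rate.
- **Omitting a baseline covariate does not cause masking.** A reader might connect the absence of days since IV diuretic to later dose changes. The two are unrelated: the first is a pre-randomization variable, and leaving it out costs precision and leaves chance imbalance unadjusted.
- **Some protection exists.** Doses are to stay fixed where possible. Total body water is measured alongside plasma volume to examine fluid shifts. Re-hospitalised patients stop study drug and join end-of-treatment procedures only if judged appropriate, which limits one route for IV diuretic use before Day 14.
- **The trial is exploratory.** Protocol 14.1 has no formal sample size calculation, and Protocol 14.7 makes the primary pharmacodynamic analysis descriptive and the ANCOVA exploratory.

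All of this stands and limits the point. It does not remove the gap: the protocol itself expects dose changes linked to study drug, and no planned table reports them by arm.

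**Conclusion.** The point holds in a limited form. Diuretic changes are recorded but not summarised by arm, on an endpoint that diuretics strongly affect, in a population nearly all of whom take them. The main analysis is not invalid and needs no replacement; the weakness is in interpreting a small or null difference. Such a result is quite possible given power of about 66% at the current size under the SAP's assumptions.

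The size is uncertain. With an assumed 20-point excess of cuts on active drug, the loss ranges from about 5% of 0.423 L (hydrochlorothiazide-sized effect, in patients without heart failure) to 14–24% (0.3–0.5 L per cut). Neither the excess nor the larger per-cut effects come from the documents. A claim that diuretic changes will mask the drug effect would go beyond them.

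The covariate point is separate and modest: an SE about 2.5–8% smaller if the interval explains 5–15% of the variance, also an assumption.

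**What to change.** **SAP 2.5.** Add one table by treatment arm: oral loop-diuretic daily dose in common equivalents at Day 1 and Day 14; numbers of patients with dose increased, decreased or stopped; and numbers given any IV diuretic after Day 1.

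**SAP 2.6.2.** Keep the as-randomised ANCOVA as the main estimate. For precision only, prespecify days from last IV diuretic to Day 1 (0 to 7) as a baseline covariate, in that model or in a sensitivity model.

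**What to avoid.** Do not use an estimate in patients without a diuretic change to separate the explanations. That subset is selected on a post-randomization variable that treatment may affect, and labelling it descriptive does not remove the selection. For the same reason, do not enter on-trial dose change as an ordinary ANCOVA covariate.

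**Cost.** SAP wording, one table, coding of dose equivalence and one degree of freedom. Drug doses and durations are already in the eCRF.
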